4.1.2 Selection of doses in the trial and dose modifications

Selection of doses in the study took into consideration the established safety profile of alteplase and was in addition based on pharmacokinetic and pharmacodynamics (PK-PD) modelling results [[c32479735-01](#)]. Doses for Part 1 were chosen to be lower than in the current indication of alteplase for massive, haemodynamic relevant PE, because COVID-19 is associated with a constant pro-inflammatory trigger of coagulation activation, leading primarily to fibrin deposition, micro-clots and non-massive PE. Dose selection was based on the fact that the fibrinogen level should not fall below 4.4 µM (150 mg/dL), which has been reported as threshold for increased risk of bleeding [[P13-13102](#)]. With both dosing regimens (A and B) the fibrinogen level is likely to remain above this threshold. Both dosing regimens are considered to deliver benefits for the treatment of the disease with an acceptable safety profile. The dose -response relationship and benefit-risk ratio of each dosing regimen will be evaluated in Part 1, and a decision will be taken after Part 1 to carry one dosing regimen into Part 2.

For dosing regimen A and B see [Table 4.1.1:1](#) above.

In Part 2 only dosing regimen B is applicable.

Dose modifications are not foreseen unless recommended by the DMC. One optional additional i.v. infusion of 0.3 mg/kg infused over 2 hours (Dosing regimen A) or 0.6 mg/kg infused over 2 hours (Dosing regimen B) can be given once on Days 2 to 5 in case of clinical worsening (as per investigator judgement). In Part 2, only dosing regimen B can be given as an additional i.v. infusion, as per investigator judgement.

4.1.3 Method of assigning patients to treatment arms

After the assessment of all eligibility criteria, each eligible patient will be randomised to treatment arms according to a randomisation plan in a 1:1:1 ratio at Visit 2a (same day as screening or day afterwards) in Part 1, and in a 2:1 randomisation rate in Part 2 via Interactive Response Technology (IRT). The appropriate medication number will be assigned and documented in the eCRF.

In Part 1 the randomisation will be stratified by the type of ventilation support (invasive mechanical / non-invasive) and in Part 2 by both type of ventilation support and by baseline D-dimer level (\geq ULN to <5-fold ULN, versus \geq 5-fold ULN), and access to the randomisation code will be controlled and documented.

Randomisation of IMV patients will be stopped when a maximum of 50 IMV patients have been randomized in Part 2.

The block sizes of the randomisation will be documented in the clinical trial report (CTR) and patients will be randomized sequentially.

Note that the medication number is different from the patient number (the latter is generated during screening via the IRT System).

4.1.4 Drug assignment and administration of doses for each patient

At Day 1, patients will be randomized to one of three treatment arms (1:1:1) in Part 1 or to one of two treatment arms (2:1) in Part 2 by the IRT.

Part 1:

9 vials will be allocated per each patient in higher dose arm and 7 vials will be allocated per each patient in lower dose arm. In case additional kits are needed reflecting calculated amount needed per body weight, site has to call IRT and register a replacement call to allocate the additionally needed kits.

Part 2:

Number of vials will be allocated per each patient depending on patient's weight in treatment arm by IRT.

Each patient kit contains:

1 vial alteplase (TPA-05) Powder for solution for injection/infusion (50 mg/vial) with 50 mL solvent for alteplase (TPA-05) powder in a box. All components are labelled in an open label fashion. Single panel labels are placed on vials and box.

The pharmacist or his/her qualified delegate will prepare the trial medication at the dose level requested by the investigator. For dose calculation and infusion rates please refer to Alteplase dosing table in [Appendix 10.5](#).

Handling and preparation of the medicinal product should be performed according to routine site procedures using aseptic techniques. Prior to the reconstitution, preparation and the infusion, the vials should be checked for any changes (e.g. color) and for the absence of particles. The lyo cake should be a white to pale yellow cake, the solution should be clear and colorless to slightly yellow. If you have any questions or concerns regarding appearance of the solution, please contact your CRA or the local Clinical Monitor.

The reconstitution should be done immediately before use.

Reconstitution can be performed with a transfer cannula (if available in the kit) or with syringe and cannula. More details on preparation, administration and in-use stability of alteplase solution will be provided in Instructions for Preparation and Administration of Alteplase 50 mg for solution for injection/infusion in ISF.

Table 4.1.4:1 Dosage and treatment schedule (Part 1)

Initial i.v. infusion (Day 1):

- Dosing regimen A: 0.3 mg/kg infused over 2 hours
- Dosing regimen B: 0.6 mg/kg infused over 2 hours

Daily long-term i.v. infusion over 12 hours from Day 1 onwards, up to at maximum Day 5:

	Dosing regimen A	Dosing regimen B
Target Dose	0.02 mg/kg/h	0.04 mg/kg/h

Optional additional i.v. infusion of 0.3 mg/kg infused over 2 hours (Dosing Regimen A) or 0.6 mg/kg infused over 2 hours (Dosing regimen B) is allowed once, on Days 2 to 5.

Part 2: One dosing regimen is carried forward based on results from Part 1 and recommendation by the DMC.

Initial i.v. infusion (Day 1):

- Dosing regimen B: 0.6 mg/kg infused over 2 hours

Daily long-term i.v. infusion over 12 hours from Day 1 onwards, up to at maximum Day 5 (plus up to 72 hours in case of unexpected interruptions):

	Dosing regimen B
Target Dose	0.04 mg/kg/h

Optional additional i.v. infusion of 0.6 mg/kg infused over 2 hours (Dosing regimen B) is allowed once during the treatment period.

4.1.5 Blinding and procedures for unblinding

4.1.5.1 Blinding

This is an open-label study, therefore no blinding will apply for patients, investigators and personnel at the site involved in trial conduct

The access to the randomisation code list will be kept restricted until it is released for analysis.

The randomisation codes will be provided to bioanalytics prior to last patient completed in each part of the trial to allow for a timely analysis of pharmacokinetic (PK) samples.

4.1.5.2 Unblinding and breaking the code

As this is an open-label trial, unblinding does not apply for the investigator and study site personnel.

Due to the requirements to report Suspected Unexpected Serious Adverse Reactions (SUSARs), it may be necessary for a representative from BI's Pharmacovigilance (PV) group to access the randomisation code for individual patients during trial conduct. The access to the code will only be given to authorised PV representatives for processing in the PV database system and not be shared further.

4.1.6 Packaging, labeling, and re-supply

The IMPs will be provided by BI or a designated Contract Research Organisation (CRO). They will be packaged and labelled in accordance with the principles of Good Manufacturing Practice. Re-supply to the sites will be managed via an IRT system, which will also monitor expiry dates of supplies available at the sites.

For details of packaging and the description of the label, refer to the ISF.

4.1.7 Storage conditions

Drug supplies will be kept in their original packaging and in a secure limited access storage area according to the recommended storage conditions on the medication label. A temperature log must be maintained for documentation.

If the storage conditions are found to be outside the specified range, the Clinical Research Associate (CRA), as provided in the list of contacts, must be contacted immediately.

4.1.8 Drug accountability

The investigator or designee will receive the investigational drugs delivered by the sponsor when the following requirements are fulfilled:

- Approval of the clinical trial protocol (CTP) by the Institutional Review Board (IRB) / Ethics Committee (EC),
- Availability of a signed and dated clinical trial contract between the sponsor and the investigational site,
- Approval/notification of the regulatory authority, e.g. Competent Authority (CA),
- Availability of the curriculum vitae of the Principal Investigator,
- Availability of a signed and dated CTP,
- Availability of the proof of a medical license for the Principal Investigator,

Investigational drugs are not allowed to be used outside the context of this protocol. They must not be forwarded to other investigators or clinics.

The investigator or designee must maintain records of the product's delivery to the trial site, the inventory at the site, the use by each patient, and the return to the sponsor or warehouse / drug distribution centre or alternative disposal of unused products. If applicable, the sponsor or warehouse / drug distribution centre will maintain records of the disposal.

These records will include dates, quantities, batch / serial numbers, expiry ('use- by') dates, and the unique code numbers assigned to the IMP and trial patients. The investigator or designee will maintain records that document adequately that the patients were provided the doses specified by this CTP and reconcile all IMPs received from the sponsor. At the time of return to the sponsor or appointed CRO, the investigator or designee must verify that no remaining supplies are in the investigator's possession.

4.2 OTHER TREATMENTS, EMERGENCY PROCEDURES, RESTRICTIONS

4.2.1 Other treatments and emergency procedures

Anticoagulant medications should be given to prevent the formation of new clots, as follows:

Alteplase arm, Day 1 to 5 (treatment period):

The investigator may choose between Option A or B:

Option A: Option A can only be applied in patients with an eGFR $\geq 30\text{ml/min}/1.73\text{m}^2$.

Low-dose LMWH in prophylactic dosages given every day at the end of long-term i.v. alteplase infusion

Recommendations for LMWH dosages (these represent examples, and other LMWHs in prophylactic dosages are also allowed):

Dalteparin 5000 U, subcutaneously (SC) once daily (OD)
Enoxaparin 40 mg (4000 U), SC OD
Fondaparinux 2.5 mg, SC OD
Nadroparin 5700 U, SC OD (patients $>70\text{ kg}$)
Nadroparin 3800 U, SC OD (patients $\leq 70\text{ kg}$)
Tinzaparin 4500 U, SC OD

In patients with moderate (creatinine clearance 30-50 ml/min/1.73m²) and mild (creatinine clearance 50-80 ml/min/1.73m²) renal impairment, careful clinical monitoring is advised.

or:

Option B: Option B can be chosen in all patients, irrespective of their eGFR.

Unfractionated heparin (UFH, e.g. 10 IU/ kg body weight/hour) concomitantly to long-term alteplase i.v. infusion, to be started immediately after initial 2 hour alteplase i.v. infusion, with a target aPTT of 1.0 to 1.5 fold of ULN according to local laboratory

[\[U99-0193, P99-02520\]](#).

UFH in a dosage of up to 5000 IU, SC BID (twice daily) can be given alternatively.

It is recommended to administer antithrombin III to patients where no further anticoagulant effects with dose increases of heparin are seen.

Alteplase arm, post treatment period (Day 5 and onwards), and SOC arm:

Option A: LMWH with target anti-Xa level according to local practice

or

Option B: Unfractionated heparin with target aPTT level according to local practice

Heparin should not be given simultaneously with the initial 2h i.v. infusion of alteplase, or at time of an *optional* additional 2h i.v. infusion of alteplase, or when an intervention needs to be performed. The additional 2h i.v. infusion of alteplase should preferably be given after UFH has been stopped for 2 hours, or ideally 12 hours after the last LMWH injection, however, these interruption intervals may not apply in an emergency situation (according to the investigator's judgement).

The interruption intervals for concomitant heparin treatment before an intervention should follow local practice. Please see product information of respective heparins for appropriate interruption intervals before intervention (for temporary interruption of alteplase, please see [Section 3.3.4.1](#)).

The anti Xa level should be monitored regularly, in patients with mild to moderate renal impairment. The aPTT level should be monitored at least daily and preferably more frequently, while given concomitantly with alteplase.

Occurrence of heparin-induced thrombocytopenia (HIT) must result in cessation of UFH or LMWH without recommencement regardless of treatment assignment. Use of an acceptable alternative agent is required in this instance as clinically indicated. Occurrence of HIT has to be reported as adverse event (AE).

Glucocorticoid treatment

Current or scheduled use of systemic (intravenous or oral) corticosteroid therapy should be included in the SOC regimen (e.g. 6 mg of dexamethasone orally) for up to 10 days or until hospital discharge. As patients in the alteplase treatment arm should also receive best possible SOC, this recommendation applies in the vs. non-invasive alteplase arm as well.

Total daily dose equivalencies to dexamethasone 6 mg are provided in [Appendix 10.6](#).

Standard of Care (SOC) arm

SOC includes any supportive measures applied in hospital, specifically on an ICU, such as for example the use of non-invasive or invasive ventilation, oxygen masks, haemodynamic support, if needed, sedation, as well as medical therapies commonly used in patients suffering from ARDS or its complications. SOC should include best possible treatment regimen established locally and should be in line with current guidelines for COVID-19 ARDS treatment.

For additional recommended SOC therapies please refer to [Appendix 10.6](#).

Recommendations before the start of alteplase:

- Arterial lines and central venous catheters, tubes (e.g. for intubation and feeding) and drains (e.g. pleural and abdominal) should be placed at least 6 hours before starting the first treatment with alteplase.
- A delay of the alteplase treatment of approximately 6 hours after the insertion of the last line/catheter is recommended to allow for complete hemostasis (this time-period can be extended to up to 24 hours after complicated interventions)
- Before the start of the very first alteplase infusion, there should have been a time period of at least 10 hours since the last LMWH (S.C.) administration to ensure no significant overlap of the LMWH and alteplase.

Emergency procedures

Management of Bleeding during Alteplase Treatment:

- In case of bleeding, the alteplase infusion can be interrupted up to a maximum of 72 hours.
- A restart is possible, if complete haemostasis is achieved, and if lab results support a restart (fibrinogen $\geq 150\text{mg/dL}$, haemoglobin is stable, anti-Xa 4 hours after s.c. administration is < 0.5 , or aPTT ratio is < 1.5 -fold of upper limit of normal).
- In case of interruptions of more than 12 hours, the time-windows for subsequent long-term infusions move accordingly, and the last long-term infusion may be given later than day 5 in the study. In total, up to 5x long-term infusions (of 12 hours each) can be given.

Management of serious bleeding events:

In case of serious bleeding, in particular cerebral or pulmonary haemorrhage, the fibrinolytic therapy must be discontinued, and concomitant heparin administration should be terminated immediately. Administration of protamine should be considered if unfractionated heparin has been administered. In patients who fail to respond to these conservative measures, judicious use of transfusion products may be indicated. Transfusion of cryoprecipitate, fresh frozen plasma, and platelets should be considered with clinical and laboratory reassessment after each administration. A target fibrinogen level of 1g/L (100 mg/dL) is desirable with cryoprecipitate infusion. Antifibrinolytic agents should also be considered.

Beyond patient-specific risk factors for bleeding, the bleeding risk can be estimated by the plasma fibrinogen level. Fibrinogen will be monitored daily during the treatment period with alteplase, and if the level falls below 150 mg/dL , the investigator should interrupt the alteplase infusion.

The alteplase infusion can be restarted, if fibrinogen recovers to $\geq 150\text{ mg/dL}$ during the following 72 hours.

In case of bleeding, intervention or surgery, the treatment with alteplase may require a temporary interruption or permanent discontinuation of alteplase, according to the investigator's discretion and the severity of the bleed. While a major bleeding may in general require a temporary interruption or premature discontinuation of alteplase, minor bleeds may not lead to changes in study drug application. For details on temporary interruption of alteplase, please see [Section 3.3.4.1](#).

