1.4.2 Risks

Bleeding events

Fibrinolytic treatment always harbours the risk of bleeding events. Depending on the anatomical location and severity of bleeding, the bleeding can be life threatening or even turn out fatal. The bleeding risk is potentially augmented when combining alteplase with anticoagulants or platelet inhibitor due to the combination of fibrinolysis, anticoagulation and/or platelet inhibition. The bleeding risk of alteplase also differs in relation to dose and rate. High doses of alteplase given at high rates increases bleeding risk. Low levels of fibrinogen ($<100 \text{ mg/dL}$) have also been identified to increase bleeding risk in relation to alteplase.

The bleeding risk can be partially estimated from the plasma level of fibrinogen. Due to its relative fibrin-specificity, alteplase results in a modest decrease of the circulating plasma fibrinogen levels to about 60% at 4 hours, which is generally reverted to more than 80% after 24 hours. Plasminogen and alpha-2-antiplasmin decrease to about 20% and 35% respectively after 4 hours and increase again to more than 80% at 24 hours [P86-5233]. A marked and prolonged decrease of the circulating fibrinogen level is only seen in few patients [P89-46753]. A plasma level of fibrinogen below 150 mg/dL has been associated with an elevated risk of bleeding [P13-13102]. The bleeding risk can be minimized by intensive monitoring of plasma fibrinogen levels and establishing stopping criteria or by dose reduction.

Vasculature health of the patient seem to play a major role in the bleeding risk. Confounding conditions affecting the vasculature health include high blood pressure, T2DM and advanced age. These conditions are considered patient-related risk factors for bleeding.

Alteplase administered intravenously carries a risk of bleeding and the extent of this risk is multifactorial (e.g. dose, weight, age, gender, blood pressure, diabetes) [P15-13160]. The highest number of bleeding events were seen in trials involving acute ischemic stroke patients, where the reported complications with alteplase total doses (up to 90 mg) given over

60 minutes were symptomatic intracerebral haemorrhage (6%) and other major haemorrhage (2%). Minor haemorrhage (e.g. bleeding at site of venepuncture) accounting for 20-25%.

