Cardiovascular: hypotension, bradycardia GI: nausea, vomiting, GI tract bleeding Haematologic: spontaneous bleeding, bone marrow depression Musculoskeletal: musculoskeletal pain Respiratory: Pulmonary edema Skin: bruising, flushing Other: fever, edema, phlebitis	More detailed description see IB, Section 7.6	Timely detection, evaluation, and follow-up of laboratory alterations in selected laboratory parameters to ensure patients' safety. ECG monitoring in ICU, repeated ECGs. Monitoring for bleeding including neurological assessment to rule out intracranial haemorrhage. Monitor hypersensitivity reactions such as angioedema, profound hypotension, rash, urticaria. Supportive treatment for bleeding including infusion therapy, red blood cell (RBC) and FFP transfusion. In case of hypersensitivity glucocorticoids, antihistamines, and adrenaline (epinephrine) address acute hypersensitivity. Intubation readiness

Clinical Trial Protocol

Page 29 of 140

Proprietary confidential information © 2022 Boehringer Ingelheim International GmbH or one or more of its affiliated companies

Table 1.4.2:1

Overview of trial-related risks (cont)

Clinical events		
Minor bleeding particularly traumatic –at site of venepuncture		Supportive treatment, and use caution during suction, measurement of plasma fibrinogen levels
Major bleeding including intracerebral haemorrhage or bleeding from a critical organ	Common	Measurement of plasma fibrinogen levels, recommendation to stop alteplase infusion, and administer fibrinogen concentrate or cryoprecipitate, if fibrinogen is <150 mg/dL and other supportive treatment including i.v. tranexamic acid should be considered
Hypersensitivity reactions (e.g. rash, urticaria, bronchospasm, angio-oedema, hypotension, shock).	Rare	Anti-allergic medications
Serious anaphylaxis	Very rare	Treat per local protocols and stop further administration of medication
Other risks		
Additional blood samples	Bleeding related to venipuncture	Compression
Transfusion of blood products, fibrinogen or supportive treatment like i.v. tranexamic acid.	Related to bleeding event. Anaphylaxis due to transfusion.	Treatment as per local protocols and product information

Risk evaluation in relation to COVID-19:

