1.4.3 Discussion

Consideration of therapies that are not recognized for this indication but of potential benefit, such as fibrinolytic agents, is warranted in this unprecedented public health emergency of COVID-19.

The bleeding risk described in the literature typically include high dosages of alteplase (up to 90 to 100 mg given as infusion over 1-3 hours) and the concurrent use of therapeutic antithrombotics. However, the alteplase short-term infusion dosages being used in this study (0.3 mg/kg/2h or 0.6 mg/kg/2h) are lower than those used in studies for MI, massive PE and stroke. Additionally, by the low dose during long-term infusion over 12 hours, the rapid inactivation of alteplase in the circulation is projected to be associated with plasma fibrinogen levels well above the threshold of 150 mg/dL, which are known to be linked to the risk of bleeding [[c32479735-01; P13-13102](#)]. The safety results from Phase II (part 1) of the current trial were generally comparable across the treatment groups, except for bleeding events, which are a known side effect of alteplase. In Phase II, mainly non-major bleeding events were observed, and some of them were related to interventions. Additional risk minimization strategies to avoid intervention-related bleeding events have accordingly been implemented for Part 2, phase III of the study.

The bleeding risk is predicted from the plasma fibrinogen level which provides a measure of the alteplase absorbed. This will be monitored and if the level falls below 150 mg/dL, alteplase has to be temporarily interrupted. Beside the extent of fibrinogen breakdown, D-Dimer levels, thrombocytopenia, the prolongation of the activated partial thromboplastin time (aPTT) will be monitored continuously. Furthermore, elevated blood pressure as a risk of intracranial hemorrhage and the co-administration of ACE inhibitors related to the risk of angioedema will be monitored.

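### For a serious bleed, Section 4.2.1 calls a fibrinogen target of 100 mg/dL desirable, while Table 1.4.2:1 recommends fibrinogen replacement below 150 mg/dL; the two passages are not reconciled

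*Protocol*

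**What the plan says.** Two passages of the current protocol attach a fibrinogen level to replacement therapy in a bleeding patient.

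- **Table 1.4.2:1 (trial-related risks).** For the event "Major bleeding including intracerebral haemorrhage or bleeding from a critical organ", the mitigation column gives a "recommendation to stop alteplase infusion, and administer fibrinogen concentrate or cryoprecipitate, if fibrinogen is <150 mg/dL".
- **Section 4.2.1 (management of serious bleeding events).** This paragraph opens with "In case of serious bleeding, in particular cerebral or pulmonary haemorrhage, the fibrinolytic therapy must be discontinued". Heparin is to be stopped as well. For patients who do not respond to these first measures, it allows transfusion products with reassessment after each one, and then says: "A target fibrinogen level of 1g/L (100 mg/dL) is desirable with cryoprecipitate infusion".

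The protocol also describes fibrinogen levels as markers of risk. Section 1.4.2 says "A plasma level of fibrinogen below 150 mg/dL has been associated with an elevated risk of bleeding", and the same section names levels under 100 mg/dL as raising bleeding risk with alteplase. Section 1.4.3 projects that fibrinogen will stay "well above the threshold of 150 mg/dL, which are known to be linked to the risk of bleeding". Section 4.1.2 bases dose selection on the same 150 mg/dL, "which has been reported as threshold for increased risk of bleeding". Sections 3.3.4.1 and 4.2.1 use 150 mg/dL as the level for interrupting and restarting the alteplase infusion.

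**The concern.** A target is where replacement may be considered sufficient; a trigger is where replacement is called for. When the target is lower than the trigger, treatment can be judged complete at a level that still calls for treatment. Here both passages cover intracerebral bleeding and both name cryoprecipitate, so a clinician with such a patient can be guided by either one.

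What is at stake is consistent management of the most serious expected harm of the study drug. Section 3.3 plans 110 to 130 sites in about 22 countries with roughly 2 to 3 patients each, so few sites will gain enough experience of their own to settle the ambiguity. They will depend on the text.

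**Working it through.** No sample size, power or error rate is involved. The check is a unit conversion followed by a comparison of the two passages.

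**1. Are the two units in Section 4.2.1 consistent?** 1 g/L = 1000 mg per 10 dL = 100 mg/dL. They agree. A level of 150 mg/dL would be 1.5 g/L, so 100 mg/dL is not a conversion slip.

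**2. How far apart are the levels?** 150 − 100 = 50 mg/dL. The target is 100/150 = 67% of the replacement trigger.

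**3. Do the passages cover the same patient?** The table speaks of major bleeding and Section 4.2.1 of serious bleeding. Intracerebral haemorrhage is named in the first and cerebral haemorrhage in the second, so for that bleed the overlap is explicit. Both name cryoprecipitate.

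**4. What does each passage imply, by fibrinogen level?**

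| Fibrinogen (mg/dL) | Table 1.4.2:1 | Section 4.2.1, serious bleeding | Consistent? |
|---|---|---|---|
| Below 100 | Replacement recommended | Below the desirable target | Yes at the start; reaching 100 can still leave the patient under the table's trigger |
| 100 to below 150 | Replacement recommended | Target already met | No |
| 150 or above | No replacement on this criterion | Target already met | Yes |

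Two illustrations: a patient at 120 mg/dL is due for replacement under the table and at target under Section 4.2.1. A patient raised from 80 to 105 mg/dL has met the Section 4.2.1 target and is still below the table's trigger.

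**5. Does any other passage settle it?** No. Sections 1.4.3 and 4.1.2 call 150 mg/dL the risk threshold, but they concern expected levels and dose selection. Section 1.4.2 mentions both levels and does not say when either one governs. Section 1.4.1 mentions fibrinogen concentrate for bleeding without giving a level.

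**The case against.** The strongest reply is that these are not two binding rules. Section 4.2.1 calls its target desirable, and the table gives a recommendation. Section 4.2.1 does not tell anyone to withhold replacement between 100 and 150 mg/dL, and it asks for reassessment after each product. A site that replaces below 150 mg/dL breaches neither passage. A trigger and a target are also different kinds of instruction, and 100 mg/dL is not an isolated figure, because Section 1.4.2 names it as a risk level too.

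All of this stands, and it limits the point to unclear advisory text. It does not remove the mismatch: a desirable end point below a recommended starting point remains incoherent, and naming two risk levels does not tell a site which one to use.

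A reader might infer three stronger claims that the documents do not support.

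- **That the interruption and restart rules also conflict with the target.** They govern whether alteplase is given, not whether fibrinogen is replaced, and in serious bleeding Section 4.2.1 requires fibrinolytic therapy to be discontinued.
- **That the major bleeding endpoint would shift with the passage a site follows.** The transfusion criterion in Section 5.2.5.1 counts units of blood or packed cells, not cryoprecipitate or fibrinogen concentrate. Both fibrinogen passages apply once a bleed has occurred, and a symptomatic intracranial bleed already qualifies as major by its location. An indirect effect through later red-cell use would be speculation.
- **That the number affected can be read from the expected number of major bleeds.** With 140 + 32 = 172 planned alteplase patients and an assumed risk of 5% to 20%, one gets 0.05 × 172 ≈ 9 to 0.20 × 172 ≈ 34. That range counts all assumed major bleeds. An affected patient would also need fibrinogen in the disputed band and, under Section 4.2.1, failure of the first measures.

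**Conclusion.** The inconsistency is real and narrow. It lies between one cell of Table 1.4.2:1 and one sentence of Section 4.2.1, and the direct contradiction covers fibrinogen from 100 to below 150 mg/dL in a patient with a serious bleed. The overlap is certain for intracerebral haemorrhage. For other bleeds it depends on reading major and serious as the same class.

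The number of patients affected cannot be derived, because the documents give no distribution of fibrinogen at the time of a bleed. Section 3.3.2 now admits patients from the lower limit of normal, where the upper limit was previously required (Section 11.3), so low values may be more common in Part 2 than in Part 1. How much more common is not stated.

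The point does not touch randomisation, the confirmatory hypotheses or their analysis. It deserves correction because it is a safety instruction that many low-recruiting sites would use, and because correcting it is cheap. No view is taken on which level is right.

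**What to change.** Reconcile Table 1.4.2:1 with the serious-bleeding paragraph of Section 4.2.1. Either one consistent fibrinogen rule governs replacement in serious bleeding, or the text states explicitly when each level applies. The wording should also make clear whether major and serious bleeding mean the same thing in these two places. The sponsor's clinical experts should decide the content, and the site instructions should carry the same wording. The cost is about one sentence in the protocol and a matching line in the site instructions; no analysis changes.
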